3.1 Aims

The Catalyst (*Carfilzomib-Dex in AL Amyloidosis treatment*) Trial aims to assess the safety and tolerability of KTD (Carfilzomib-Thalidomide-Dexamethasone) using the phase 1 dose escalating component to define the maximum tolerated dose (MTD) and recommended dose (RD) and the expansion cohort to further assess the safety and tolerability and to gain an understating of efficacy to allow design for further trials.

Primary:

Dose escalation

To define the MTD and RD of Carfilzomib used in combination with Thalidomide and Dexamethasone in patients with relapsed or refractory AL amyloidosis

Dose expansion

To further assess the safety and tolerability of KTD at the RD of Carfilzomib identified in the dose escalation phase

Secondary:

To make a preliminary assessment of the activity of KTD in patients with relapsed refractory AL amyloidosis

3.2 Trial Activation

Leeds Clinical Trials Research Unit (CTRU) will ensure that all trial documentation has been reviewed and approved by all relevant bodies and that the following have been obtained prior to activating the trial:

- Research Ethics Committee approval.
- Clinical Trial Authorisation from the Medicines and Healthcare products Regulatory Agency (MHRA)
- Adequate funding for central co-ordination
- Adoption into NIHR portfolio
- NHS permission
- Confirmation of sponsorship
- Adequate insurance provision

4.0 Selection of Sites/Site Investigators

4.1 Site (*Regional Haematology Centre*) selection

In this protocol trial “site” refers to the hospital where trial-related activities are conducted.

Sites must be able to comply with:

- Trial treatments, clinical care, follow up schedules and all requirements of the trial protocol
- Requirements of the Research Governance Framework and the Medicines for Human Use (clinical trials) Act (SI 2004/1031 and all amendments)
- Monitoring requirements, as outlined in the protocol (section 16.0 and Trial Monitoring Plan)
- Data collection requirements including adherence to CRF submission timelines as per section 12.0
- Sample collection and processing requirements

4.1.1 Selection of Principal Investigators and other investigators at sites

Sites must have an appropriate Principal Investigator (PI) i.e. a health care professional authorised by the site, ethics committee and regulatory Authority to lead and coordinate the work of the trial on behalf of the site. Other investigators at site wishing to participate in the trial must be trained and approved by the PI. All investigators must be medical doctors and have experience of treating amyloidosis.

4.1.2 Training requirements for site staff

All site staff must be appropriately qualified by education, training and experience to perform the trial related duties allocated to them, which must be recorded on the site delegation log.

CVs for all staff must be kept up-to-date, signed and dated and copies held in the Investigator Site File (ISF). An up-to-date, signed copy of the CV for the PI must be forwarded to CTRU upon request.

GCP training is required for all staff responsible for trial activities. The frequency of repeat training may be dictated by the requirements of their employing institution, or 2 yearly where the institution has no policy, and more frequently when there have been updates to the legal or regulatory requirements for the conduct of clinical trials.

4.2 Site initiation and Activation

4.2.1 Site Initiation

Before a site is activated, the CTRU trial team will arrange a site initiation with the site which the PI, the pharmacy lead and site research team must attend. The site will be trained in the day-to-day management of the trial and essential documentation required for the trial will be checked.

The site initiation will be performed by site visit or teleconference.

4.2.2 Required documentation

The following documentation must be submitted by the site to CTRU prior to a site being activated by the CTRU trial team:

- Trial specific Feasibility/Site Registration Form (identifying relevant local staff and contact details)
- All relevant institutional approvals (e.g. local NHS permission)
- A completed authorised personnel log and pharmacy personnel log that is signed and dated by the PI
- A copy of the PI’s current CV that is signed and dated
- A copy of the PI’s GCP certificate
- PI declaration that is signed and dated
- Lead pharmacist declaration that is signed and dated
- Local lab ranges and lab accreditations
- Trial specific prescriptions & labels

In addition, the following agreement must be in place:

- a fully signed model non-commercial agreement (mNCA) between the Sponsor and the relevant institution (usually a NHS Trust)

4.2.3 Site activation

Once the CTRU trial team at Leeds has received all required documentation and the site has been initiated, **a site activation email** will be issued to the PI and other key site contacts, at which point:

- If the site in question is the UK National Amyloidosis Centre (UK NAC), they may start to approach patients
- If the site is a Regional Haematology Centre (RHC), the UK NAC can begin to refer patients to them.

Once the site has been activated by CTRU, the PI is responsible for ensuring:

- adherence to the most recent approved version of the protocol
- all relevant site staff are trained in the protocol requirements
- appropriate recruitment and medical care of patients in the trial
- timely completion and return of CRFs (including assessment of all adverse events)
- prompt notification and assessment of all serious adverse events
- that the site has facilities to provide **24 hour medical advice** for trial patients

Please note, for the CATALYST trial, all patients will be approached by the UK National Amyloidosis Centre (UK NAC) and referred by UK NAC to a suitable Regional Haematology Centre (RHC)/Site. No patients may be referred to an RHC/Site that is not activated by Leeds CTRU. Leeds CTRU will provide UK NAC with an up to date list of activated RHCs.

5.0 Informed consent

The UK NAC must ensure that all patients have been given the current approved version of the patient information sheet(s), are fully informed about the trial and have confirmed their willingness to take part in the trial by signing the current approved consent form.

The UK NAC must assess a patient's ability to understand verbal and written information in English and whether or not an interpreter would be required to ensure fully informed consent. If a patient requires an interpreter and none is available, the patient should not be considered for the trial.

The UK NAC PI, or, where delegated by the PI, other appropriately trained site staff (trained on the study protocol, Patient Information Sheet and are GCP trained), are required to provide a full explanation of the trial and all relevant treatment options to each patient prior to trial entry. During these discussions the current approved patient information sheet for the trial should be discussed with the patient (including the aims, methods, possible benefits and possible disadvantages of taking part). The patient will be allowed as much time as needed to consider and discuss their participation in the trial. Patients will be given the option to take the patient information sheet and consent form away and return it by post (this is standard practice at UK NAC). Upon receipt at UK NAC, the consent form must be checked for completeness and then signed by the appropriate investigator. Dated entries for this consent process must be recorded in the patient's medical notes. No clinical trial procedures will be conducted prior to obtaining consent. Consent will not denote enrolment to the trial. If new safety information results changes in the significant risk/benefit the consent will be reviewed and updated and patients will be given an opportunity to re-consent to participating in the study.

Healthcare professionals have specific obligations that must be followed when prescribing or dispensing thalidomide. As such, patients must be fully educated on the risks of thalidomide in accordance with the Celgene Pregnancy Prevention Programme. This should be done by an authorised member of staff at the research centre at the time the patient is given a full verbal explanation of the trial.

Written informed consent on the current approved version of the consent form for the trial must be obtained before any trial-specific procedures are conducted.

UK NAC staff are responsible for:

- Checking that the correct (current approved) version of the patient information sheet and consent form are used
- Checking that information on consent forms is complete and legible
- Checking that the patient has completed/initialled all relevant sections and signed and dated the consent form
- Checking that an appropriate member of staff has countersigned and dated the consent form to confirm that they provided information to the patient
- Checking that an appropriate member of staff has made dated entries in the patient's medical notes relating to the informed consent process (i.e. information given, consent signed etc.)
- Giving the patient a copy of their signed consent form, patient card and Red Flag card
- Adding details of all consented patients to the informed consent form log
- Following registration and confirmation of eligibility: adding the patient trial number to all copies of the consent form, which should be filed in the patient's medical notes and investigator site file
- Sending a copy of the completed consent form to the CTRU and the appropriate RHC following registration (see 4.1 & 6.1)

The original signed consent form must be stored at the UK NAC, one copy forwarded to the CTRU, one copy forwarded to the Regional Haematology Centre (RHC), and a copy given to the patient.

The right of the patient to refuse to participate in the trial without giving reasons must be respected. All patients are free to withdraw at any time. Also refer to section 14.0 (Withdrawal of patients).

5.1 Referral of patients to Regional Haematology Centres

Following consent and registration (see section 7.1), patients will be referred to the appropriate Regional Haematology Centre (RHC). The choice of RHC will be discussed and agreed with the patient during their UK NAC visit.

UK NAC are responsible for forwarding a copy of the signed informed consent form (fax or email is acceptable) to the RHC in order that trial specific activities may be undertaken, with an additional copy being sent to the CTRU.

Following referral the RHC will contact the patient to arrange their first visit (to include confirmation of eligibility to the trial). This visit must be within 28 days of the patient's registration.

Authorised members of the study team at the RHC should give the participant an opportunity to ask any further questions about the trial and to check they are still willing to take part in the trial.(as part of the re-confirmation of eligibility visit)

6.0 Selection of Patients

6.1 Pre-treatment Evaluation

Patients referred to the UK NAC with AL amyloidosis are routinely sent a 'General Clinical Research Information Sheet' with their UK NAC appointment letter. Nationally, patients are followed up at the UK NAC as part of standard practice, where a full 'Amyloid Evaluation' is undertaken, usually over a period of two days; follow up visits are approximately 6 monthly. The Amyloid Evaluation includes Serum Amyloid Protein component (SAP) scintigraphy, echocardiography, full haematological, biochemical and urine examinations for evidence of organ dysfunction, clonal disease, a bone marrow (if indicated) and cardiac biomarkers. This standard amyloid assessment will form the baseline pre-treatment evaluation. The patient will also have a blood test to check hepatitis B status. Patients who may receive thalidomide treatment or other chemotherapy outside of the trial have this test as standard of care. Any UK patient with a diagnosis of systemic AL amyloidosis who has relapsed disease is potentially eligible for entry into the trial (see 6.3 for patient eligibility).

Please see protocol section 11 for assessment summary and Appendix 6 for diagnostic sample requirements and investigations.

UK NAC will confirm eligibility for the trial and consent patients, following this, registration will take place at Leeds CTRU. All registered patients will have a brief pre-treatment evaluation to reconfirm eligibility at their allocated RHC (Regional Haematology Centre).

6.2 Screening Log

A screening log must be maintained by the UK NAC and kept in the UK NAC CATALYST Site File. This must record each patient screened for the trial/all patients identified with proven systemic AL amyloidosis and the reasons why they were not registered in the trial if this is the case.

The log must be sent to Leeds CTRU from UK NAC when requested, with patient identifiers removed prior to sending.

Individual RHC sites will not be asked to maintain a screening log.

6.3 Patient Eligibility

There will be no exception to the eligibility requirements at the time of registration. Ensuring patient eligibility is the responsibility of the UK NAC PI or other delegated Investigator(s). Queries in relation to the eligibility criteria must be addressed prior to calling/faxing registration. Patients are eligible for the trial if all the inclusion criteria are met and none of the exclusion criteria applies.

6.3.1 Inclusion Criteria

Patients with the following characteristics are eligible for this study:

1. Aged 18 years or greater
2. Diagnosis of systemic AL amyloidosis with
 - i. exclusion of genetic mutations associated with hereditary amyloidosis and immunohistochemical exclusion of AA and TTR amyloidosis as appropriate
 - ii. Amyloid-related organ dysfunction or organ syndrome (see Appendix 2)
3. Measurable clonal disease
4. Clonal relapse after previous chemotherapy or autograft stem cell transplant OR refractory clonal disease to previous chemotherapy or stem cell transplant
5. Capable of providing written, informed consent and willing to follow study protocol
6. Life expectancy \geq 6 months
7. ECOG performance status of 0-2
8. Platelet count \geq $50 \times 10^9/l$
9. Neutrophil count \geq $1 \times 10^9/l$
10. Haemoglobin \geq 8g/dL
11. Bilirubin < 2 times or Alkaline phosphatase < 4 times upper limit of normal.
12. Female participants of child-bearing potential must have a negative pregnancy test prior to treatment and agree to use dual methods of contraception for the duration of the study and for 30 days following completion of study. Male participants must also agree to use a barrier method of contraception for the

duration of the study and for 90 days following completion of study if sexually active with a female of child-bearing potential. Women who could become pregnant must have taken precautions not to become pregnant for 1 month before the start of the study. Because of the increased risk of venous thromboembolism in patients, combined oral contraceptive pills are not recommended.

13. Participants must be willing to comply with the Celgene pregnancy prevention programme for Thalidomide

6.3.2 Exclusion Criteria

Patients with the following characteristics are ineligible for this study (see Appendices for definitions):

1. Overt symptomatic multiple myeloma
2. Amyloidosis of unknown or non-AL type
3. Localised AL amyloidosis (in which amyloid deposits are limited to a typical single organ, for example the bladder or larynx, in association with a clonal proliferative disorder within that organ)
4. Trivial or incidental AL amyloid deposits in the absence of a significant amyloid-related organ syndrome (e.g., isolated carpal tunnel syndrome)
5. Refractory to or progressive disease with an IMiD and proteasome inhibitor combination
6. Allogeneic stem cell transplantation
7. Solid organ transplantation
8. Severe peripheral or autonomic neuropathy causing significant functional impairment that, in the investigator's opinion, may interfere with protocol adherence
9. eGFR <20ml/min
10. Ejection fraction < 40% or NYHA class III or IV heart failure or uncontrolled hypertension that concerns the investigator
11. Severe pulmonary Hypertension that, in the investigator's opinion, may interfere with protocol adherence
12. Advanced Mayo stage III disease as defined by hs-Troponin T >0.07 and NT-proBNP >700 pMol/L OR NT-proBNP >1000 pMol/L OR supine SBP <100 mm of Hg
13. Myocardial infarction in the preceding 6 months or unstable angina or conduction abnormalities uncontrolled by medication or devices
14. Concurrent active malignancies, except surgically removed basal cell carcinoma of the skin or other in situ carcinomas
15. Pregnant, lactating or unwilling to use adequate contraception
16. Systemic infection unless specific anti-infective therapy is employed
17. Known or suspected HIV infection
18. Contraindication to any of the required concomitant drugs or supportive treatments
19. Any other clinically significant medical disease or condition or psychiatric illness that, in the Investigator's opinion, may interfere with protocol adherence or a participant's ability to give informed consent
20. Previous experimental agents within 3 months before the date of registration
21. Known allergies to Carfilzomib, Thalidomide or Dexamethasone
22. Positive hepatitis B viruses (HBV) test

6.3.3 Pregnancy and Birth Control

The risks to the human embryo or foetus from exposure to Carfilzomib are currently unknown. Thalidomide is teratogenic. The ability of corticosteroids to cross the placenta varies between individual drugs, however, Dexamethasone readily crosses the placenta. Administration of corticosteroids to pregnant animals can cause abnormalities of foetal development including cleft palate, intra-uterine growth retardation and affects on brain growth and development. There is no evidence that corticosteroids result in an increased incidence of congenital abnormalities, such as cleft palate/lip in man. However, when administered for prolonged periods or repeatedly during pregnancy, corticosteroids may increase the risk of intra-uterine growth retardation. Hypoadrenalism may, in theory, occur in the neonate following prenatal exposure to corticosteroids but usually resolves spontaneously following birth and is rarely clinically important. Corticosteroids may pass into breast milk, although no data are available for Dexamethasone. Infants of mothers taking high doses of systemic corticosteroids for prolonged periods may have a degree of adrenal suppression.

All patients will have to comply with the Thalidomide pregnancy prevention programme.

Pregnancy Testing

All women of child bearing potential who are at risk of becoming pregnant must undergo a pregnancy test prior to commencing the trial drugs and prior to start of each cycle.

Sterilisation of either partner is not usually regarded as completely reliable enough to ensure that pregnancy can never occur.

A woman of childbearing potential is a sexually mature woman (i.e. any female who has experienced menstrual bleeding) who has not:

- undergone a hysterectomy or bilateral oophorectomy/salpingectomy
- been postmenopausal for 24 consecutive months (i.e. who has not had menses at any time in the preceding 24 consecutive months without an alternative medical cause)

Contraceptive advice

Due to the effects of the trial treatment during pregnancy and lactation, patients must consent to use one of the following acceptable methods of contraception during the study and for 30 days (in the case of female participants) or 90 days (in the case of male participants) after the end of the study treatment. Women who could become pregnant must have taken precautions not to become pregnant for 1 month before the start of the study

Acceptable methods of effective contraception for this trial are:

- Established use of oral methods of contraception. Because of the increased risk of venous thromboembolism in patients, combined oral contraceptive pills are not recommended.
- Placement of an intrauterine device (IUD) or intrauterine system (IUS).
- Barrier methods of contraception: condom or occlusive cap (diaphragm or cervical/vault caps) with spermicidal foam/gel/film/cream/suppository. The use of barrier contraceptives should always be supplemented with the use of a spermicide. The following should be noted:
 - Failure rates indicate that, when used alone, the diaphragm and condom are not highly effective forms of contraception. Therefore the use of additional spermicides does confer additional theoretical contraceptive protection.
 - However, spermicides alone are inefficient at preventing pregnancy when the whole ejaculate is spilled. Therefore, spermicides are not a barrier method of contraception and must not be used alone.
- Male sterilisation (with appropriate post-vasectomy documentation of the absence of sperm in the ejaculate). For female patients, the vasectomised male partners must be the sole partner for that patient. Please note that sterilisation is not usually regarded as completely reliable enough on its own to ensure that pregnancy can never occur.
- Absolute and continuous abstinence: When this is in line with the preferred and usual lifestyle of the patient. Please note that periodic abstinence (e.g. calendar, ovulation, symptothermal, post-ovulation methods) and withdrawal are not acceptable methods of contraception.

Because of the potential for serious undesirable effects in breast-fed infants, lactation should be discontinued during trial treatment. Women should not breastfeed for 3 months following their last dose of study treatment. The method(s) of contraception used must be stated in the patient medical notes.

Should a pregnancy occur, either to a female patient or to a female partner of a male patient while on the trial Leeds CTRU must be informed immediately (Please refer to section 13.5 Pregnancy for details on the reporting procedure).

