Inclusion & Exclusion criteria	
Inclusion Criteria
 
Patients with the following characteristics are eligible for this study:
 
 1. Aged 18 years or greater 2. Diagnosis of systemic AL amyloidosis with 3. exclusion of genetic mutations associated with hereditary amyloidosis and immunohistochemical exclusion of AA and TTR amyloidosis as appropriate 4. Amyloid-related organ dysfunction or organ syndrome 5. Measurable clonal disease 6. Clonal relapse after previous chemotherapy or autograft stem cell transplant OR refractory clonal disease to previous chemotherapy or stem cell transplant 7. Capable of providing written, informed consent and willing to follow study protocol 8. Life expectancy \geq 6 months 9. ECOG performance status of 0-2 10. Platelet count \geq $50 \times 10^9/l$ 11. Neutrophil count \geq $1 \times 10^9/l$ 12. Haemoglobin \geq 8g/dL 13. Bilirubin $<$2 times or Alkaline phosphatase $<$4 times upper limit of normal 14. Female participants of child-bearing potential must have a negative pregnancy test prior to treatment and agree to use dual methods of contraception for the duration of the study and for 30 days following completion of study. Male participants must also agree to use a barrier method of contraception for the duration of the study and for 90 days following completion of study if sexually active with a female of child-bearing potential. Women who could become pregnant must have taken precautions not to become pregnant for 1 month before the start of the study

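### Section 6.3.3 asks for one listed contraceptive method, but inclusion criterion 12 requires two for women of child-bearing potential and a barrier for men with such partners

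*Protocol*

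**What the plan says.** Inclusion criterion 12 in Protocol section 6.3.1 requires women of child-bearing potential to "agree to use dual methods of contraception for the duration of the study and for 30 days following completion of study". It adds: "Male participants must also agree to use a barrier method of contraception". For men the period runs to 90 days after the study, and the requirement applies to those sexually active with a woman of child-bearing potential. The summary in section 1.1 repeats the rule: "Female participants of child-bearing potential must have a negative pregnancy test prior to treatment and agree to use dual methods of contraception". Section 6.3 allows no exceptions to eligibility at registration, and criterion 13 requires willingness to comply with the thalidomide pregnancy prevention programme.

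Section 6.3.3 gives a different rule in its contraceptive advice: "patients must consent to use one of the following acceptable methods of contraception during the study". The same sentence covers both sexes, with 30 days for women and 90 for men after the end of treatment. Five separate entries follow:

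1. oral contraception ("Established use of oral methods of contraception", with combined pills not recommended)
2. an intrauterine device or system
3. a barrier with spermicide
4. male sterilisation with documented absence of sperm
5. continuous abstinence

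The section twice cautions about sterilisation. Under pregnancy testing it says: "Sterilisation of either partner is not usually regarded as completely reliable enough to ensure that pregnancy can never occur". Within the list entry itself it says: "Please note that sterilisation is not usually regarded as completely reliable enough on its own". It also requires the method or methods used to be recorded in the medical notes.

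The SAP sets no contraceptive rule. It only names pregnancy among the items monitored during the trial.

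**The concern.** The same patients are given two rules. Criterion 12 sets a number of methods for women and a type of method for men. Section 6.3.3, the protocol's only list of acceptable methods, asks for any one entry and makes no distinction by sex beyond the length of the period. It also lists male sterilisation as an acceptable choice while warning that sterilisation should not be relied on alone.

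What is at stake is participant safety. Section 6.3.3 describes thalidomide as teratogenic and the embryo-foetal risk of carfilzomib as unknown. Thalidomide is taken daily for up to six cycles. Consent and thalidomide education are handled through the national centre (section 5.0), while treatment is given at regional centres (section 8.1.1), with 15 sites planned. Different staff could therefore rely on different sections.

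**Working it through.** No design calculation applies. The check is a comparison of texts, followed by a search for anything that settles the difference.

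**Step 1. Each listed method, used alone, against both rules.**

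| Method used alone | Section 6.3.3 | Criterion 12, woman of child-bearing potential | Criterion 12, man sexually active with such a woman |
|---|---|---|---|
| Oral | Accepted | Fails: one method | Fails: no barrier |
| IUD/IUS | Accepted | Fails: one method | Fails: no barrier |
| Barrier with spermicide | Accepted | Unclear: not stated whether this is one method or two | Meets |
| Male sterilisation | Accepted, with a caution | Fails: one method | Fails: no barrier |
| Continuous abstinence | Accepted | Not counted | Condition does not arise |

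The clear conflicts are oral, IUD/IUS and male sterilisation: 3 of 5. Criterion 12 makes no exemption for vasectomised men.

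**Step 2. Length of the period covered by section 6.3.3, from first dose and without delays.** Cycles last 28 days, with a maximum of six. Patients whose disease has not responded by the end of three cycles come off trial treatment (section 9.4).

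- Six cycles: 6 × 28 = 168 days; 168 + 30 = 198 days for women; 168 + 90 = 258 days for men.
- Three cycles: 3 × 28 = 84 days; 84 + 30 = 114 days for women; 84 + 90 = 174 days for men.

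These figures give the duration of the rule. They do not estimate exposure.

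**Step 3. Number of patients.** Planned enrolment is at most 18 + 20 = 38 before replacements. The documents do not say how many would be women of child-bearing potential or men with such partners, so no affected number can be derived.

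**Step 4. Does any other text settle the difference?**

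- The pregnancy prevention programme is required in sections 5.0, 6.3.1 (criterion 13), 6.3.3, 9.3.3 and 13.5, and section 9.1 routes thalidomide supply through its controlled process. None of these gives the number of methods.
- Exclusion criterion 15 refers only to contraception being adequate.
- No section says whether criterion 12 or section 6.3.3 takes precedence.

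**Step 5. What is checked after entry?** The assessments itemised in sections 11.1.2 and 11.2 include a pregnancy test but no contraception item. However, sections 7.1 and 11.1.2 require the regional centre to confirm that the patient still meets the eligibility criteria, which include criteria 12 and 13. Section 6.3.3 requires the notes to record what is used. Neither safeguard says how many methods the patient needs.

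**The case against.** The strongest reply is that criterion 12 already governs. Its agreement covers the whole study and 30 or 90 days beyond, so it cannot be dismissed as a registration-day formality. Criterion 5 requires willingness to follow the protocol. The national centre confirms eligibility and sends a checklist, the trials unit checks the criteria before registration (section 16.1), and the regional centre reconfirms. Thalidomide supply is controlled, and pregnancy tests are supervised and timed to prescription (section 11.0 table notes). A woman using two listed methods satisfies both texts, so section 6.3.3 could be read as the menu and criterion 12 as the number required.

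Most of this stands, and it limits the practical risk. It does not remove the contradiction, because section 6.3.3 itself states a number, and that number is one. The menu reading requires the reader to ignore that word.

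A reader might infer that the trial permits patients to take thalidomide on a single method, or that contraception goes unchecked after entry. The documents do not support either inference. Criterion 12 is binding and covers the full period, eligibility is reconfirmed, and methods must be recorded. The programme's content is not in the documents and the consent pages are not in the copy reviewed, so how patients are actually counselled cannot be judged.

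A reader might also see a gap in the two starting points for the 30- and 90-day periods: completion of the study in criterion 12, end of treatment in section 6.3.3. Both give at least 30 or 90 days after treatment, so this is a matter of tidiness only.

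**Conclusion.** The contradiction is real and sits in operative text. Read alone, section 6.3.3 would accept an oral method, an IUD/IUS or vasectomy as sole contraception during treatment with a teratogenic drug; criterion 12 would not. The size is three of five listed methods, for an unknown share of at most 38 planned patients.

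The conclusion rests on the wording of the two sections and on the absence of any rule of precedence or any stated number of methods for the programme. It does not depend on an assumption about site behaviour. Confidence is high for the mismatch; the likelihood of harm cannot be estimated from the documents and is reduced by the safeguards above. It should be corrected because the possible harm is irreversible and the correction is cheap. No endpoint or statistical conclusion is affected.

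**What to change.** First check both texts against the pregnancy prevention programme. Then replace the one-method wording in section 6.3.3 with the criterion 12 rule:

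- Women of child-bearing potential use two listed methods, unless practising continuous abstinence as the list defines it. Without this exception, an abstinent woman would literally need a second method.
- Men sexually active with a woman of child-bearing potential use a barrier method, including men who have had a vasectomy.
- Male sterilisation is not sufficient alone.

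Check that the patient information sheet says the same. Optionally, use one starting point for the 30- and 90-day periods in sections 1.1, 6.3.1 and 6.3.3, for example the last dose of any trial drug.

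The cost is a small wording amendment and one document check. Sample size, DLT rules and analysis stay as they are.
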